Treatment assignment will be stratified via an Interactive Voice Response System (IVRS)/or an Interactive Web Response System (IWRS) based on (1) concomitant use of oral corticosteroids and (2) previous exposure to immunosuppressants (eg, 6-mercaptopurine [6-MP], azathioprine [AZA], or methotrexate [MTX]). The number of subjects with previous exposure to immunosuppressants is targeted to comprise no more than 50% of the subjects enrolled, and no less than 30%.

The study will consist of 5 phases:

- Screening Phase – up to 4 weeks
- Double-blind Placebo-controlled Phase – Weeks 0 to 12
- Blinded Active-treatment Phase – Weeks 12 to 52
- Extension Phase – Weeks 52 to 104
 - The 52-week extension is an active-treatment phase and henceforth will be referred to as the Extension Phase for the remainder of the document. The Extension Phase was blinded prior to the implementation of Amendment 4. Following the implementation of Amendment 4, the Extension Phase will be open-label and all subjects will receive 30 mg BID as of their next visit.
- Post-treatment Observational Follow-up Phase – The 4-week period after the last dose of investigational product (IP)

Double-blind Placebo-controlled Phase

Eligible subjects will enter the Double-blind, Placebo-controlled Phase at the Baseline Visit (Week 0/Visit 2). Subjects will be randomly assigned to study treatment as described above. With the aim to mitigate potential dose-related side effects associated with apremilast, such as

headache and gastrointestinal (GI) disturbances, apremilast-treated subjects will be dose-titrated in 10-mg/day increments over the first 8 days of treatment. All subjects will receive blister cards of identical appearance to maintain blinding (Table 5). Subjects will continue to receive the treatment assigned at baseline for 12 weeks.

Blinded Active-treatment Phase

Following 12 weeks of treatment, subjects will enter the Blinded Active-treatment Phase. At the Week 12 visit, subjects will be evaluated for clinical improvement based on the TMS. The endoscopy subscore assessed by the investigator will be used for the calculation of the Week 12 TMS.

Subjects who achieve at least a 20% decrease from baseline in the TMS at Week 12 will receive the following IP between the Week 12 Visit and the Week 52 Visit:

- Subjects who were randomized to apremilast (30 mg BID or 40 mg BID) at baseline will continue to receive the treatment assigned at baseline.

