Eligible subjects will enter the Double-blind Placebo-controlled Phase for 12 weeks, at the Baseline Visit (Week 0, Visit 2). Subjects will be randomly assigned to study treatment as described above. With the aim to mitigate potential dose-related side effects associated with apremilast, such as headache and gastrointestinal (GI) disturbances, apremilast-treated subjects will be dose-titrated in 10-mg/day increments over the first 8 days of treatment (Table 5). All subjects will receive blister cards of identical appearance to maintain blinding. Subjects will continue to receive the treatment assigned at baseline for 12 weeks.

Blinded Active-treatment Phase

Following 12 weeks of treatment, subjects will enter the Blinded Active-treatment Phase for 40 weeks. At the Week 12 visit, subjects will be evaluated for clinical improvement based on the TMS. The endoscopy subscore assessed by the investigator will be used for the calculation of the Week 12 TMS.

Subjects who achieve at least a 20% decrease from baseline in the TMS at Week 12 will receive the following IP between the Week 12 Visit and the Week 52 Visit:

- Subjects who were randomized to apremilast (30 mg BID or 40 mg BID) at baseline will continue to receive the treatment assigned at baseline.
- Subjects who were randomized to placebo at baseline will be re-randomized to receive apremilast (30 mg BID or 40 mg BID) and will be dose-titrated in 10-mg/day increments over the first 8 days of treatment (Table 5).

Subjects who do not achieve at least a 20% decrease from baseline in the TMS at Week 12 will receive the following IP until the Week 52 Visit:

- Subjects who were randomized to apremilast 30 mg BID at baseline will be re-assigned apremilast 40 mg BID, with no dose titration.
- Subjects who were randomized to apremilast 40 mg BID at baseline will continue to receive apremilast 40 mg BID.
- Subjects who were randomized to placebo at baseline will be re-randomized to receive apremilast (30 mg BID or 40 mg BID) and will be dose-titrated in 10-mg/day increments over the first 8 days of treatment (Table 5).

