8.2. Treatment Administration and Schedule

Tablets will be taken by mouth twice daily, in the morning (AM) and in the evening (PM), approximately 12 hours apart, with no food restrictions. With the aim to mitigate potential dose-related side effects associated with apremilast such as headache and GI disturbances, apremilast-treated subjects will be dose-titrated in 10-mg/day increments over the first 8 days of treatment in the Double-blind Placebo-controlled Phase.

After 12 weeks of treatment, apremilast-treated subjects who do not achieve at least a 20% decrease from baseline in the TMS, will receive apremilast 40 mg BID. Placebo subjects, will be re-randomized to receive apremilast 30 mg BID or 40 mg BID, and will be dose-titrated prior to receiving active treatment (Table 5). However, in order to maintain the blind for the treatment assigned at baseline, all subjects will receive blister cards of identical appearance during both titration periods. In the absence of a 40-mg tablet, two 20-mg tablets or identically appearing placebo will be taken by those subjects randomized to the 40-mg BID apremilast dose group.

Subjects who complete 52 weeks of treatment and have a Mayo endoscopy score ≤ 1 will be eligible to participate in the 52-week Extension Phase and receive apremilast treatment. With the implementation of Amendment 4, subjects entering the Extension Phase from the Week 52 Visit will receive apremilast 30 mg BID. Subjects currently in the Extension Phase who are receiving apremilast 40 mg BID will be switched to 30 mg BID at the next scheduled visit.

Table 5: Treatment Schema for Dose Titration

| Treatment Group | Treatment Schema for Dose Titration ^a | | | | | | | | | | | | | | | |
|-----------------|--|---------|---------|---------|---------|---------|---------|---------|---------|---------|---------|---------|---------|---------|--------------------|---------|
| | Day 1 | | Day 2 | | Day 3 | | Day 4 | | Day 5 | | Day 6 | | Day 7 | | Day 8 + Thereafter | |
| | AM | PM | AM | PM | AM | PM | AM | PM | AM | PM | AM | PM | AM | PM | AM | PM |
| 30 mg BID | 10 mg A | 10 mg P | 10 mg A | 10 mg A | 10 mg A | 10 mg P | 10 mg P | 10 mg P | 10 mg P | 10 mg P | 10 mg P | 10 mg P | | | | |
| | 20 mg P | 20 mg P | 20 mg P | 20 mg P | 20 mg P | 20 mg A | 20 mg A | 20 mg A | 20 mg A | 20 mg A | 20 mg P | 20 mg P | 20 mg P | 20 mg P | 20 mg P | 20 mg P |

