| | 20 mg P | 20 mg P | 20 mg P | 20 mg P | 20 mg P | 20 mg P | 20 mg P | 20 mg P | 20 mg P | 20 mg P | 20 mg P | 20 mg P | 20 mg P | 20 mg P | 20 mg P | 20 mg P |
| | 30 mg P | 30 mg P | 30 mg P | 30 mg P | 30 mg P | 30 mg P | 30 mg P | 30 mg P | 30 mg P | 30 mg A | 30 mg A | 30 mg A | 30 mg A | 30 mg A | 30 mg A | 30 mg A |
| 40 mg BID | 10 mg A | 10 mg P | 10 mg A | 10 mg A | 10 mg A | 10 mg P | 10 mg P | 10 mg P | 10 mg P | 10 mg P | 10 mg P | 10 mg P | | | | |
| | 20 mg P | 20 mg P | 20 mg P | 20 mg P | 20 mg P | 20 mg A | 20 mg A | 20 mg A | 20 mg A | 20 mg A | 20 mg P | 20 mg P | 20 mg P | 20 mg P | 20 mg A | 20 mg A |
| | 20 mg P | 20 mg P | 20 mg P | 20 mg P | 20 mg P | 20 mg P | 20 mg P | 20 mg P | 20 mg P | 20 mg P | 20 mg P | 20 mg P | 20 mg P | 20 mg P | 20 mg A | 20 mg A |
| | 30 mg P | 30 mg P | 30 mg P | 30 mg P | 30 mg P | 30 mg P | 30 mg P | 30 mg P | 30 mg P | 30 mg P | 30 mg A | 30 mg A | 30 mg A | 30 mg A | 30 mg P | 30 mg P |
| Placebo | 10 mg P | 10 mg P | 10 mg P | 10 mg P | 10 mg P | 10 mg P | 10 mg P | 10 mg P | 10 mg P | 10 mg P | 10 mg P | 10 mg P | | | | |
| | 20 mg P | 20 mg P | 20 mg P | 20 mg P | 20 mg P | 20 mg P | 20 mg P | 20 mg P | 20 mg P | 20 mg P | 20 mg P | 20 mg P | 20 mg P | 20 mg P | 20 mg P | 20 mg P |
| | 20 mg P | 20 mg P | 20 mg P | 20 mg P | 20 mg P | 20 mg P | 20 mg P | 20 mg P | 20 mg P | 20 mg P | 20 mg P | 20 mg P | 20 mg P | 20 mg P | 20 mg P | 20 mg P |
| | 30 mg P | 30 mg P | 30 mg P | 30 mg P | 30 mg P | 30 mg P | 30 mg P | 30 mg P | 30 mg P | 30 mg P | 30 mg P | 30 mg P | 30 mg P | 30 mg P | 30 mg P | 30 mg P |

A = Apremilast; BID = twice daily; P = Placebo.

Note: In the absence of a 40 mg tablet, subjects will take 2 x 20 mg apremilast tablets or placebo BID.

^a Active apremilast subjects will be dose titrated during the first 8 days of the study (Week 0, Day 1); At the week 12 Visit, placebo subjects will be re-randomized to apremilast 30 mg or 40 mg BID and will be dose titrated for the first 8 days of treatment.

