8.3. Method of Treatment Assignment

After the informed consent is signed, subjects will be assigned a subject identification number using a centralized IVRS/IWRS. At the Baseline Visit, a centralized schema will be applied to assign subjects who meet the inclusion/exclusion criteria in a 1:1:1 ratio to receive either apremilast 30 mg PO BID or 40 mg PO BID, or placebo.

Subjects will be randomized by following two stratification parameters:

- Concomitant use of oral corticosteroids
- Previous exposure to immunosuppressants (eg, 6-MP, AZA, or MTX)

The number of subjects with previous exposure to immunosuppressants is targeted to comprise no more than 50% of the subjects enrolled, and no less than 30%.

Following 12 weeks of treatment, subjects will enter the Blinded Active-treatment Phase. At the Week 12 visit, subjects will be evaluated for clinical improvement based on the TMS. The endoscopy subscore assessed by the investigator will be used for the calculation of the Week 12 TMS.

Subjects who achieve at least a 20% decrease from baseline in the TMS at Week 12 will receive the following IP between the Week 12 Visit and the Week 52 Visit:

- Subjects who were randomized to apremilast (30 mg BID or 40 mg BID) at baseline will continue to receive the treatment assigned at baseline.
- Subjects who were randomized to placebo at baseline will be re-randomized to receive apremilast (30 mg BID or 40 mg BID) and will be dose-titrated in 10-mg/day increments over the first 8 days of treatment (Table 5).

Subjects who do not achieve at least a 20% decrease from baseline in the TMS at Week 12 will receive the following IP until the Week 52 Visit:

- Subjects who were randomized to apremilast 30 mg BID at baseline will be re-assigned apremilast 40 mg BID, with no dose titration.
- Subjects who were randomized to apremilast 40 mg BID at baseline will continue to receive apremilast 40 mg BID.
- Subjects who were randomized to placebo at baseline will be re-randomized to receive apremilast (30 mg BID or 40 mg BID) and will be dose-titrated in 10-mg/day increments over the first 8 days of treatment (Table 5).

Subjects who participate in the Extension Phase will receive apremilast 30 mg BID. With the implementation of Amendment 4, subjects currently in the Extension Phase who are receiving 40 mg BID will be switched to 30 mg BD at the next scheduled visit.

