#### **Blinded Active-treatment Phase**

Following 12 weeks of treatment, subjects will enter the Blinded Active-treatment Phase for 40 weeks. At the Week 12 visit, subjects will be evaluated for clinical improvement based on the

TMS. The endoscopy subscore assessed by the investigator will be used for the calculation of the Week 12 TMS.

Subjects who achieve at least a 20% decrease from baseline in the TMS at Week 12 will receive the following IP between the Week 12 Visit and the Week 52 Visit:

- Subjects who were randomized to apremilast (30 mg BID or 40 mg BID) at baseline will continue to receive the treatment assigned at baseline.
- Subjects who were randomized to placebo at baseline will be re-randomized to receive apremilast (30 mg BID or 40 mg BID) and will be dose-titrated in 10-mg/day increments over the first 8 days of treatment.

Subjects who do not achieve at least a 20% decrease from baseline in the TMS at Week 12 will receive the following IP until the Week 52 Visit:

- Subjects who were randomized to apremilast 30 mg BID at baseline will be re-assigned apremilast 40 mg BID, with no dose titration.
- Subjects who were randomized to apremilast 40 mg BID at baseline will continue to receive apremilast 40 mg BID.
- Subjects who were randomized to placebo at baseline will be re-randomized to receive apremilast (30 mg BID or 40 mg BID) and will be dose-titrated in 10-mg/day increments over the first 8 days of treatment.

In order to maintain the blind for the treatment assigned at baseline, all subjects will receive blister cards of identical appearance during the titration period beginning at Week 12. However, for subjects continuing on the dosage of apremilast assigned at baseline, and for subjects who are not undergoing dose titration (as noted above), the IP included in the “titration” portion of the blister card will include the total daily dose of apremilast (30 or 40 mg BID) and will not include the dose titration.

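### Does the 40 mg BID titration in Table 5 depart from the 10-mg/day wording in a way that needs a change to the plan?

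*Protocol*

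**What the plan says.** Protocol 8.2 states that "apremilast-treated subjects will be dose-titrated in 10-mg/day increments over the first 8 days of treatment in the Double-blind Placebo-controlled Phase". The same rule stands in the Protocol Summary and in protocol 4.1 and 8.3, and 4.1 and 8.3 point to Table 5 in the same sentence. SAP 4.1 repeats it without the table; for placebo subjects re-randomized at Week 12 it says they "will be dose-titrated in 10-mg/day increments over the first 8 days of treatment".

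Table 5 lists every tablet, active (A) or placebo (P), morning and evening. Three rows of the 40 mg BID block matter here:

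- 30-mg row, Day 6 AM to Day 8 PM: "30 mg A | 30 mg A | 30 mg A | 30 mg A | 30 mg P | 30 mg P"
- second 20-mg row, same six intakes: "20 mg P | 20 mg P | 20 mg P | 20 mg P | 20 mg A | 20 mg A"
- first 20-mg row, Day 5 PM to Day 8 AM: "20 mg A | 20 mg P | 20 mg P | 20 mg P | 20 mg P | 20 mg A"

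The table note says that 40 mg is made up of two 20-mg tablets. The footnote gives the length of the titration but allows no exception to the 10-mg step.

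**The concern.** The sentence is written in mg per day, and two sections present Table 5 as its detail. A reader would expect the daily total to rise by 10 mg each day until the target is reached. On Days 6 to 8 the 40 mg BID block does not do that.

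Titration is there to reduce headache and gastrointestinal effects. If text and table describe different schedules, the record of what subjects took in the first week is uncertain. Protocol 4.2 says the study should inform the design of later studies in this population, so a wrong description could be carried forward. Someone reading only the SAP would not see the table at all.

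**Working it through.** **Inputs.** All cells come from the 40 mg BID block of Table 5. The 20-mg and 30-mg rows each have 16 cells. The 10-mg row has 12, with Days 7 and 8 blank in all three arms; no 10-mg tablet is active after Day 3, so the blanks do not affect the totals.

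**Daily totals.** Dose per intake = sum of the active tablet strengths; daily total = AM + PM.

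| Day | AM (mg) | PM (mg) | Total (mg) | Change from day before |
|---|---|---|---|---|
| 1 | 10 | 0 | 10 | – |
| 2 | 10 | 10 | 20 | +10 |
| 3 | 10 | 20 | 30 | +10 |
| 4 | 20 | 20 | 40 | +10 |
| 5 | 20 | 20 | 40 | 0 |
| 6 | 30 | 30 | 60 | +20 |
| 7 | 30 | 30 | 60 | 0 |
| 8 | 40 | 40 | 80 | +20 |

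No weight is put on Day 5. In the 30 mg BID block, Day 5 PM shows a 20-mg and a 30-mg tablet both active, giving 20 + 50 = 70 mg on Day 5 and then 60 mg on Day 6. That makes the Day 5 PM column doubtful as printed.

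**What the sentence implies.** It gives no starting dose and no daily figures. Assume the table's Day 1 total of 10 mg and seven steps of 10 mg: 10, 20, 30, 40, 50, 60, 70, 80. This series is an inference and appears nowhere in the documents.

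**Does the sentence hold for the other arm?** No. The 30 mg BID target is 2 × 30 = 60 mg/day, and the table shows 60 mg on Days 6, 7 and 8. A daily rise of 10 mg through Day 8 would overshoot that target.

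**Intake by intake.** Compare each 40 mg BID intake with the same intake the day before. On Day 7 the changes are 0 and 0; on Day 8 they are +10 and +10. Over the whole block no AM or PM intake rises by more than 10 mg on that comparison. A 10-mg step therefore describes the single intakes, though not the daily totals.

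**Could one column explain it?** With the blank cells left blank, equal 10-mg steps over Days 6 to 8 need at least three changed cells. All three can sit in the Day 7 PM column: 30-mg A to P, and both 20-mg P to A. Day 7 would then be 30 + 40 = 70 mg, and Days 6 to 8 would read 60, 70, 80.

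**Size in cumulative dose.** Sum of Days 1–8, plus 80 mg for each later day:

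| | Days 1–8 | To Day 14 (+ 6 × 80 = 480) | To Day 84 (+ 76 × 80 = 6080) |
|---|---|---|---|
| Table as printed | 340 | 820 | 6420 |
| Table with Day 5 = 50 mg | 350 | 830 | 6430 |
| Eight equal steps | 360 | 840 | 6440 |

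As printed, the gap from equal steps is 20/840 = 2.4% at Day 14 and 20/6440 = 0.3% at Day 84. With Day 5 at 50 mg it is 10/840 = 1.2% and 10/6440 = 0.2%.

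**Does any analysis use these figures?** SAP 9.1 measures exposure in weeks. SAP 9.2 counts tablets taken against tablets intended. That count ignores which tablets are active: each arm has 12 intakes × 4 tablets + 4 intakes × 3 tablets = 60 tablets over Days 1–8. SAP 12.1.2 uses event counts and person-time. The primary analysis in SAP 11.3.1 compares arms as randomized. None takes a milligram dose.

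**The case for a change.** The strongest case for acting is that the unit is written as mg per day, the rule is repeated throughout both documents, and two sections tie it to the table. The Day 6–8 pattern is also coherent in itself: 30 mg twice daily for two days, then two 20-mg tablets twice daily, as the table note describes. Three misplaced cells would be a lot if they arose separately. A check would cost little.

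Part of this stands. As printed, the daily totals do not match the sentence, and the intake-by-intake reading does not remove that.

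The rest is weaker. Table faults tend to run down a column, so three cells in one column may be a single fault, and the Day 5 PM column is already doubtful. The 60, 70, 80 series is constructed from the sentence, and the sentence is loose for both arms. Under protocol 4.1 and 8.4, dosing came from pre-packed blister cards of identical appearance, so the wording governed nobody's intake. Adverse events in the first two weeks reflect what the cards contained, however the schedule is described. The appeal to future studies is general and points to no result of this trial that would differ.

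**Conclusion.** This is a clerical inconsistency. For 40 mg BID on Days 6 to 8 the table as printed shows daily steps of 0 and +20 mg where the text says 10 mg. The two places must be reconciled in the record against what the cards contained, after checking the Day 5 PM and Day 7 PM columns. Nothing here says which schedule is right.

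No change to the design, conduct or analysis follows. Protocol 4.1.2 and 4.1.3 show that the placebo-controlled phase is complete and that all subjects are in the Extension Phase once Amendment 4 takes effect, so both titration periods have passed. Power, the Week 12 endpoint and the safety tables are the same under either description. The gap is at most 20 mg, or 0.3% of cumulative dose by Day 84.

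This rests on three assumptions: the table cells are read correctly, the 10 mg on Day 1 is the starting point for the equal-step series, and no redacted analysis takes its milligram dose from the sentence.

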8.3. Method of Treatment Assignment

After the informed consent is signed, subjects will be assigned a subject identification number using a centralized IVRS/IWRS. At the Baseline Visit, a centralized schema will be applied to assign subjects who meet the inclusion/exclusion criteria in a 1:1:1 ratio to receive either apremilast 30 mg PO BID or 40 mg PO BID, or placebo.

Subjects will be randomized by following two stratification parameters:

- Concomitant use of oral corticosteroids
- Previous exposure to immunosuppressants (eg, 6-MP, AZA, or MTX)

The number of subjects with previous exposure to immunosuppressants is targeted to comprise no more than 50% of the subjects enrolled, and no less than 30%.

Following 12 weeks of treatment, subjects will enter the Blinded Active-treatment Phase. At the Week 12 visit, subjects will be evaluated for clinical improvement based on the TMS. The endoscopy subscore assessed by the investigator will be used for the calculation of the Week 12 TMS.

Subjects who achieve at least a 20% decrease from baseline in the TMS at Week 12 will receive the following IP between the Week 12 Visit and the Week 52 Visit:

- Subjects who were randomized to apremilast (30 mg BID or 40 mg BID) at baseline will continue to receive the treatment assigned at baseline.
- Subjects who were randomized to placebo at baseline will be re-randomized to receive apremilast (30 mg BID or 40 mg BID) and will be dose-titrated in 10-mg/day increments over the first 8 days of treatment (Table 5).

Subjects who do not achieve at least a 20% decrease from baseline in the TMS at Week 12 will receive the following IP until the Week 52 Visit:

- Subjects who were randomized to apremilast 30 mg BID at baseline will be re-assigned apremilast 40 mg BID, with no dose titration.
- Subjects who were randomized to apremilast 40 mg BID at baseline will continue to receive apremilast 40 mg BID.
- Subjects who were randomized to placebo at baseline will be re-randomized to receive apremilast (30 mg BID or 40 mg BID) and will be dose-titrated in 10-mg/day increments over the first 8 days of treatment (Table 5).

Subjects who participate in the Extension Phase will receive apremilast 30 mg BID. With the implementation of Amendment 4, subjects currently in the Extension Phase who are receiving 40 mg BID will be switched to 30 mg BD at the next scheduled visit.

Designated study personnel at the investigational sites will be assigned password-protected, coded identification numbers that give them authorization to call into the IVRS/IWRS to randomize subjects. The system will present a menu of questions by which the study personnel will identify the subject and confirm eligibility. When all questions have been answered, the

IVRS/IWRS will assign a randomization identification number. Confirmation of the randomization will be sent via fax to the investigational site, Celgene and/or its representative.

During the study visits, the pharmacy or authorized study personnel at the investigational site will dispense coded IP kits in accordance with the randomization number assigned by the interactive IVRS/IWRS.

8.4. Packaging and Labeling

All IP, including placebo and apremilast tablets, will be supplied by Celgene to the principal investigator as blister cards for the duration of the study.

Apremilast will be provided in blister cards as 10-mg, 20-mg, or 30-mg tablets in the clinical image. Tablets will be taken by mouth twice daily, morning and evening, approximately 12 hours apart, with no food restrictions.

The label(s) for IP will include sponsor name, address and telephone number, the protocol number, IP name, dosage form and strength (where applicable), amount of IP per container, lot number, expiry date (where applicable), medication identification/kit number, dosing instructions, storage conditions, and required caution statements and/or regulatory statements as applicable. Additional information may be included on the label as applicable per local regulations.

